#### *Simple Reaction Time*

A repeated measures mixed-model design will be employed. A total of up to three groups (Device vs. no device vs concussion) will be examined using a 3 x 2 (group by time point; pre-season vs. post-season) ANOVA.

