**(1) ABSTRACT:**

Significant morbidity, mortality, and related costs are caused by traumatic brain injury (TBI). A simple, effective, and lightweight device worn by athletes or war fighters in the field, designed to mitigate TBI resulting from blast trauma or concussive events, would save lives, and the huge costs incurred for life-treatment of surviving victims. An externally-worn medical device (the Device) that applies mild jugular vein compression according to the principle of the Queckenstedt Maneuver, is being developed by Q30 Sports Science, LLC (Q30). Preliminary research suggests that the Device has the potential to reduce the likelihood of TBI. The currently developed collar (Smith 2009, Smith and Fisher 2011, Smith and Fisher 2011, Smith 2012) has been approved for studies in humans (IRB 2013-2240) and the results indicate safety for use during high demand and maximal exertion activities. Regarding safety, the externally worn collar is meticulously designed to mimic the body's own omohyoid muscle actions upon the jugular veins that will provide similar pressure and volume increases not to surpass that of a yawn or the mere act of just lying down.

This study will investigate the effectiveness of this device in high school athletes playing a non-helmeted sport such as soccer. Athletes participating in this study will be randomly assigned to one of two groups: 1) Device wearing during the season or 2) Non-device wearing during the season. This study will focus on the use and effectiveness of the device solely in females, as male football and hockey players have previously been investigated. All participants will be outfitted with an adhesive patch-like accelerometer (which will be placed behind the ear (*Xpatch-X2 Biosystems* [http://www.x2biosystems.com/x2\\_x\\_patch/](http://www.x2biosystems.com/x2_x_patch/)) which will measure the magnitude of every impact to the head sustained by the athlete. Effectiveness of the device will be determined via differences in longitudinal brain imaging and functional testing following competitive soccer participation. A subset of athletes who report a diagnosed concussion will also receive additional brain neuroanatomical and neurophysiological testing within a week following the diagnosed concussive event. At each of these time points participants will also undergo various neurocognitive assessments outlined below.

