**(6) SELECTION & RECRUITMENT OF PARTICIPANTS:**

We will recruit up to 150 study participants. The participants (age 14-19 years old) will be recruited from a local school district and local sports clubs and teams. Participants will be recruited using a top-down approach. We have gained the consent and the cooperation of the school district administrations. Presentations and letters from the research team will be given to each participating school to detail the participation requirements and study risks.. Questions regarding participation will be answered during the presentations or through e-mail or phone. Participants will be contacted via telephone to further explain the study, answer any additional questions and to enroll them in the study. The participants and parents/guardians who voluntarily agree to participate will be scheduled to complete the pre-participation testing. The participant and parent/guardian will read and sign the “Consent to Participate in a Research Study” form, approved by the Institutional Review Board of Cincinnati Children’s Hospital. If the participant and parent/guardian does not read or sign the form, they will not participate in the study. Once the potential study participants/school teams are identified, they will be allocated to one of two groups: 1) Device wearing during the season or 2) Non-device wearing during the season. This research does not mandate that the participant maintains participation in their sport. The desire to participate in the sporting event is an independent, personal decision separate from the decision to enter into this study. If any athlete chooses to stop participation in the sporting activity then they will also be withdrawn from the study, due to no longer meeting inclusion criteria.

Inclusionary criteria include:

- Female

- Normal healthy volunteer
- Able to provide written consent
- Must be 14 years or older and a participant on a high school soccer team

Exclusionary criteria include:

- Unable to provide written consent
- History of neurological deficits, previous cerebral infarction, or severe head trauma as indicated through pre-season screening:
- Medical contraindications to restriction of venous outflow via the internal jugular veins (known increased intracerebral pressure, metabolic acidosis or alkalosis)
- Glaucoma (Narrow Angle or Normal Tension)
- Hydrocephalus
- Recent penetrating brain trauma (within 6 months)
- Known carotid hypersensitivity

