***Statistical considerations.*** The data analysis will begin with a review of descriptive statistics for all major variables and all major subgroupings of variables in the data set. For the inferential methods, we will use a number of different generalized linear modeling techniques, including linear regression models. All analyses will be conducted using SAS® version 9.3 (SAS Inst, Cary, NC), or Mplus (Muthén, 2007). Initial analyses will be undertaken to inspect data for errors, inconsistencies, and incomplete information. This will include examining the data with simple frequency tables and dot plots for univariate data and scatter plots and multi-way dot plots for bivariate and multivariate data. Data anomalies that cannot be resolved by the Biostatistical/data management team will be sent as queries via

email to the project investigator for clarification and/or correction. During the verification process, outlying values will be corrected if necessary. Incomplete information will be corrected and the project investigator will receive updates. To summarize bivariate relationships among predictors and between predictors and outcomes, Chi-square of Fisher's exact test or Spearman's rank correlation coefficient, will be used, as appropriate. For reporting inferential statistics, such as differences in rates or means, 95 percent confidence intervals will be used extensively to quantify degree of clinical efficacy. Unless otherwise stated, statistical tests are considered two-sided and a .05 significance level is used. All models will be adjusted for potential independent predictor variables but will be limited to the number of predictors we can fit in a regression model while maintaining a valid and reliable model. Candidate predictors include amount of playing time, amount of practice time, previous mTBI, weight, age and height. Collinearity will be examined. Linearity assumptions will be checked and transformations examined. In those cases, a log transformation, polynomial terms, or restricted cubic splines will likely be used to relax the assumption of linearity in the regression models. We will remove the nonlinear terms or transformation only if the nonlinear test is non-significant with a  $p \geq .10$ . Additionally, overly-influential observations and distributional assumptions will be checked. Models will be interpreted graphically, predicted values will be examined, and appropriate significance tests will be utilized.

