***Statistical analyses.*** - Statistical analysis of outcomes measures will be done using SAS®, version 9.3 (SAS Institute, Cary, NC) and SPSS statistical software (SPSS Inc, Chicago IL). Comparisons between the testing conditions (collar vs. no collar) will be made using Analysis of Covariance, in order to control for time (pre vs post season) and condition (collar versus no collar). We will also conduct correlation analysis to test the association between imaging biomarkers (as described above) with the results obtained from the impact surveillance. The collision indices, including total number of collisions, number of collisions from front, back, left, right, top, bottom, G force, and timing of each collision will all be recorded and tested in the analysis. Secondary analysis to compare the intervention with no intervention and calculate the rates would involve a Poisson model, using an offset to account for the playing time and exposure to concussive impact for each of the study participants. We will calculate the rate and the associated 95% confidence interval. SAS®, PROC GENMOD will be used for analysis, which allows us to account for the fixed and random effects, use the appropriate link function, and the offset for amount of playing time exposure.

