#### *Oculomotor Measures*

Oculomotor control performance will also be compared using a 3 x 2 mixed-model ANOVA for each of the dependent variables. For smooth pursuit tracking performance, mean eye peak velocity and tracking lag will be submitted to separate 3 (group) x 2 (session) x 2 (random vs. sinusoidal task condition) mixed-model ANOVA.

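### The reaction-time and oculomotor analyses put in-season concussion into the group factor, so their stated test does not isolate the collar

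*Combined protocol and SAP*

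**What the plan says.** The Abstract sets up two groups: "Athletes participating in this study will be randomly assigned to one of two groups". Section (6) also has two, although it leaves open whether athletes or teams are allocated: "Once the potential study participants/school teams are identified, they will be allocated to one of two groups".

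Within section (9), the general paragraph on statistical analyses gives a two-condition model: "Comparisons between the testing conditions (collar vs. no collar) will be made using Analysis of Covariance". It covers outcome measures at large and sets none aside.

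Two outcome-specific subsections then follow. Simple Reaction Time: "A total of up to three groups (Device vs. no device vs concussion) will be examined using a 3 x 2", the second factor being pre-season against post-season. Oculomotor Measures: "Oculomotor control performance will also be compared using a 3 x 2 mixed-model ANOVA for each of the dependent variables", and for smooth pursuit, peak velocity and lag "will be submitted to separate 3 (group) x 2 (session) x 2 (random vs. sinusoidal task condition) mixed-model ANOVA". This second subsection does not restate the three levels. They carry over from the reaction-time text.

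Neither subsection names a device-versus-no-device contrast, defines the concussion group, or says whether a concussed athlete also stays in her allocated group. Earlier head injury is handled elsewhere, as a covariate: "Candidate predictors include amount of playing time, amount of practice time, previous mTBI, weight, age and height".

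**The concern.** Three levels of one between-athlete factor are mutually exclusive, so an athlete in the concussion level is in neither device nor no device. The Abstract, the imaging procedures in section (8) and the payment section (17) all describe concussion as something diagnosed while the athlete is in the study. The third level is therefore formed after allocation, by an event the device is intended to prevent. The number of levels also depends on whether any concussion occurs.

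With three groups and two time points, the group-by-time test has 2 df. It asks whether any of the three mean changes differ, and a few concussed athletes can drive the answer. These outcomes bear on the study's main question, because the Abstract says: "Effectiveness of the device will be determined via differences in longitudinal brain imaging and functional testing following competitive soccer participation". Station II of section (8) lists 11 oculomotor measures (5 + 2 + 4), and reaction time comes on top of these.

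**Working it through.** The plan gives no power statement, effect size or derivation for its 150 athletes, so there is no figure to reproduce. The calculation below is an illustration.

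**Inputs from the documents.** Up to 150 athletes (section 6); two-sided 0.05 (section 9); concussion rates of 0.36 per 1,000 and 4.5 per 10,000 exposures (section 3).

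**Assumptions.** Independent athletes; equal groups; 40 to 80 exposures per athlete; SD of the pre-to-post change set to 1; concussed athletes' mean change worse by s, still present at post-season.

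**1. Size of the third group.** Expected concussions = athletes × exposures × rate.
- Low: 150 × 40 × 0.00036 = 2.16
- High: 150 × 80 × 0.00045 = 5.40

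The Poisson chance of no concussion at all is exp(−2.16) = 12% down to exp(−5.40) = 0.5%. The third cell would be very small and could be empty.

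**2. Omnibus test with no collar effect.** With two time points, the group-by-time F equals a one-way F on change scores. With n₃ concussed among N = 150, the noncentrality is λ = n₃(N − n₃)/N × s², on 2 and 147 df.

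| n₃ | s = 0.25 | s = 0.5 | s = 1.0 |
|---|---|---|---|
| 2 (λ = 1.973 s²) | 5.9% | 8.8% | 21.9% |
| 4 (λ = 3.893 s²) | 6.8% | 12.9% | 39.8% |

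A two-arm t test on the same change scores, with the 4 concussed athletes kept in their allocated groups, rejects in 5% of simulated trials at each of these shifts.

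**3. Power for an assumed collar effect of 0.5 SD.**
- Omnibus, 73/73/4, concussed mean midway between the arms: λ = 2 × 73 × 0.25² = 9.125, power 76.8%.
- Omnibus, concussed mean equal to one arm mean: λ = 77 × 73/150 × 0.5² = 9.368, power 77.9%.
- 1-df contrast, 73 against 73: λ = 73/2 × 0.5² = 9.125, power 85.1%.
- 1-df comparison as allocated, 75 against 75: λ = 75/2 × 0.5² = 9.375, power 86.0%.

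If the concussed athletes do 0.25 to 1.0 SD worse than the no-device mean, the omnibus test rejects more often (81% to 94%), but partly because of them.

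**4. Bias in the collar contrast from regrouping.** Taking k more concussed athletes out of one arm of 75 than out of the other, each differing from her arm by e, moves the contrast by about k/75 × e.
- Low: 2.16 concussions split 1.08 per arm, halved to 0.54 with the device: (1.08 − 0.54)/75 × 0.5 = 0.004 SD.
- High: 2.7 in one arm, none in the other, e = 1.5: 2.7/75 × 1.5 = 0.054 SD.

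**The case against.** The strongest reply is that the ANCOVA and the ANOVAs do not conflict. The former is general, the latter are outcome-specific, and specific text normally governs. A reader might infer an outright contradiction, and the documents do not support that. Accepting the reply, however, leaves reaction time and the oculomotor measures without a named collar test. If instead both models apply, no precedence is stated. Either reading needs a correction.

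A second reply is that device and no device are explicit factor levels, and that section (9) promises 95% confidence intervals and suitable significance tests, so a pairwise contrast could follow. It could, but none is specified. The three-level factor is a stated analysis rather than a missing detail.

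A third reply is that the concussion group may be defined in text that did not survive. This is fair. The concussion follow-up paragraph in section (8) ends in a fragment, and no reaction-time procedure appears. The point is therefore limited to the available text and does not claim that the plan never defined the group.

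A reader might also take 40% as the false-positive rate for the collar. The documents do not support that. They give no figure for a deficit lasting to post-season, the rate is near nominal at 0.25 SD, and nowhere do they say that the omnibus F will be read as a collar effect.

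Finally, extra precision from adjusting for the pre-season value should not be counted as a cost of this defect, because it does not come from removing the concussion level.

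**Conclusion.** The point holds and should be fixed, with medium confidence. For reaction time and the oculomotor measures, the stated factor mixes two allocated groups with a post-allocation event, and its 2-df test does not answer whether the collar had an effect. The case rests on this structure and not on any one percentage.

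Under the assumptions above, the avoidable power loss is about 7 to 9 points at 0.5 SD when the concussed mean lies between or at the arm means. With 4 concussed and no collar effect, the omnibus test rejects in 7% to 40% of trials, depending on an unknown lasting deficit.

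A reader might infer that regrouping seriously distorts the collar estimate. It does not: the shift is at most about 0.05 SD, even with all the excess concussions in one arm. Imaging outcomes, impact correlations and the Poisson model are not affected, and no passage makes these functional measures primary.

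**What to change.** In the Simple Reaction Time and Oculomotor Measures subsections:

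- Replace the three-level factor with the two allocated groups, and keep every athlete in her allocated group whether or not she is concussed.
- Name one 1-df collar comparison as the test of the device for these outcomes. Either the collar-by-time contrast or the post-season value adjusted for the pre-season value would serve. They are different estimators, so choose one and state it the same way in the general statistical analyses paragraph.
- Use the same two-level factor in the smooth-pursuit models with task condition, and say which term carries the collar test.
- Define the concussion group and analyse it separately, labelled as a non-randomised comparison. Whether that analysis is descriptive or inferential is the sponsor's choice.
- If teams are the unit of allocation, as sections (6) and (8) allow, the chosen test must also account for team. The 85-86% power above assumes independent athletes and would not carry over.

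The change is to analysis wording only and needs no new data or visits. Its statistical cost is slight added noise from keeping concussed athletes in. In simulation with 4 concussed, power for a 0.5 SD effect falls from 86% to about 85% at a 1.0 SD deficit and 84% at 1.5 SD, a loss of about 1-2 points.

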**(5) DURATION:**

The study recruitment and intervention will occur during one season. Each participant will participate in at least 2 planned study visits that may take up to 3 hours. Data analysis will continue for a 2 year period following the final enrollment.

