### **Injury Surveillance**

*Device and Compliance Acceptance:* The study coordinator will be responsible for providing the appropriate intervention (device or no-device) to each team based on their assignment prior to the season onset. At first fitting of the collar a registered vascular technologist will utilize ultrasound to ensure that the collar fits correctly and is activated as prescribed. Following the initial fitting, each athlete will receive adequate instruction on how to properly use the device on a daily basis. Throughout the season, the coordinator will make routine visits to each team to monitor the proper usage and fitting of the device, tracking the use of the device by each athlete individually. At the end of practice/game the device will be collected by the athletic trainer and/or stored in the athlete's locked locker. The device is NOT to go home with the athlete.

*New Concussion Surveillance and Follow-up:* Each participant will be provided with an X Patch accelerometer (X2 Biosystems; Seattle, Washington) The X patch adheres to the head, just behind the ear using an adhesive patch, as seen in the image below. .

X2 is a small and durable device that is attached to the back of the neck behind the ear to track impacts, and it stores data for uploading to a PC. This X2 accelerometer accurately measures the severity of impacts by converting data such as high impact collision into usable data outputs. X2 data will be used in final analysis to normalize the exposures to potential concussive events. All impacts of greater than 10 g-force will be recorded and utilized in the post-season analyses. No one besides those approved by this IRB protocol will have access to any data. If available, video of games and practices will be used to validate and confirm head impacts recorded by accelerometers.

concussion testing completed as part of the study, will be used in making any clinical decisions for return to play.

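### Reaction-time and oculomotor outcomes are tested by a group-by-time ANOVA, which with two visits compares mean change; naming the pre-season value as a covariate would give a more precise device effect at almost no cost

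*Combined protocol and SAP*

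**What the plan says.** Four paragraphs of section (9) bear on this.

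- **Simple Reaction Time.** Up to three groups (device, no device, concussion) are to be "examined using a 3 x 2 (group by time point; pre-season vs. post-season) ANOVA". The pre-season value is thus one level of the time factor and is not a covariate.
- **Oculomotor Measures.** The same layout is carried over: "Oculomotor control performance will also be compared using a 3 x 2 mixed-model ANOVA for each of the dependent variables". Smooth pursuit adds task condition as a further two-level factor. Here too the pre-season value is a level of the session factor only.
- **Statistical analyses.** Collar versus no collar is to be compared by Analysis of Covariance, but what is said to be controlled is time (pre versus post) and condition. The pre-season value of the outcome is not named.
- **Statistical considerations.** Models are to be adjusted for predictors: "Candidate predictors include amount of playing time, amount of practice time, previous mTBI, weight, age and height". The pre-season value of the outcome is not in this list.

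On design, section (5) states: "Each participant will participate in at least 2 planned study visits". The Abstract states: "Athletes participating in this study will be randomly assigned to one of two groups". The Injury Surveillance text, however, has the coordinator provide device or no device "to each team based on their assignment prior to the season onset", and section (6) speaks of allocating participants or school teams.

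**The concern.** A group-by-time interaction with two time points uses the pre-season value in one fixed way: it subtracts it in full. That sets the slope of post-season on pre-season at 1 and carries the noise of both visits into the comparison. When r is below 1 and the two variances are equal, the best-fitting slope is r, so full subtraction over-corrects. Given a chance pre-season difference d between arms, the change estimate is off by (1−r)d in the opposite direction.

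What is at stake is precision, not validity. Enrolment is capped ("We will recruit up to 150 study participants"), recruitment and intervention fall in one season, and no power calculation is given. Lost precision therefore cannot easily be recovered with more athletes, whereas the covariate that would recover it is already part of the design.

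**Working it through.** **Inputs from the documents.** Two planned visits (section (5)). At most 150 athletes (section (6)). Significance level: "statistical tests are considered two-sided and a .05 significance level is used". Two allocated groups, described as random in the Abstract.

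**Assumptions.** The documents give no pre/post correlation r, SD, effect size, power or allocation ratio, so there is no planned figure to reproduce. I take 75 per arm, equal variance σ² at both visits, individual randomisation and no clustering, and I vary r.

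**Step 1: the identity.** On simulated data with two visits and three groups of 70, 70 and 10, the group-by-time F from the repeated-measures model was 5.4255 (p = 0.00533). The one-way ANOVA F on post-minus-pre change was also 5.4255 (p = 0.00533).

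**Step 2: the variances, per athlete.**

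- Post-season value alone: σ²
- Change: σ² + σ² − 2rσ² = 2(1−r)σ²
- Post-season adjusted for pre-season: (1−r²)σ²
- Adjusted / change: (1−r)(1+r) / [2(1−r)] = (1+r)/2
- Extra athletes needed by the change test for equal precision: 2/(1+r) − 1

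**Step 3: the numbers.** The detectable difference is (1.960 + 0.842) × √variance × √(2/75), in SD units, at 80% power. The last column is the power of the adjusted model at the difference for which the change test has 80%.

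| r | Variance ratio | Extra athletes | N adjusted matching 150 by change | Detectable difference, change / adjusted | Adjusted power |
|---|---|---|---|---|---|
| 0.3 | 0.65 | 54% | 97.5 | 0.541 / 0.436 | 93% |
| 0.5 | 0.75 | 33% | 112.5 | 0.457 / 0.396 | 90% |
| 0.7 | 0.85 | 18% | 127.5 | 0.354 / 0.327 | 86% |
| 0.8 | 0.90 | 11% | 135 | 0.289 / 0.274 | 84% |
| 0.9 | 0.95 | 5% | 142.5 | 0.205 / 0.199 | 82% |

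For example, at r = 0.5 the change test gives 2.802 × 1 × 0.1633 = 0.457, and the adjusted model gives 2.802 × √0.75 × 0.1633 = 0.396.

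Below r = 0.5 the change test is also less precise than ignoring the pre-season value: at r = 0.3 its variance is 1.4σ², against 1.0σ² for the post-season value alone.

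**Step 4: simulation check.** With 4,000 simulated trials per value of r, the variance ratios were 0.73, 0.87 and 0.97 at r = 0.5, 0.7 and 0.9, against 0.75, 0.85 and 0.95 from the formula.

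**The case against.** **The plan already names Analysis of Covariance.** This is the strongest reply, and a reader should not conclude that the plan rules out baseline adjustment. The general paragraph does make it the method for collar versus no collar, and the predictor list is introduced by a word that leaves it open. But the paragraph lists time and condition as what is controlled, which are the factors of the ANOVA, and the outcome-specific paragraphs name ANOVA. The plan is therefore unreconciled and does not name the covariate. That much of the point stands.

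**Allocation may be by team.** This also stands as a limit. If teams are allocated, the athlete-level figures are only illustrative, and either analysis has to account for team. If the arms were not formed at random, change and adjusted models can estimate different things. A claim that the change analysis has no merit would therefore go too far.

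**The gain may be small.** The oculomotor tasks use several trials per visit. If these are averaged, r may be high, and at r = 0.9 the cost is about 5%. The documents do not settle where r lies.

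**The group main effect.** A reader might infer that the plan halves the collar effect, because that term averages the two visits and the collar cannot have changed the pre-season value: (0 + δ)/2 = δ/2. The documents do not say which term is the test, and a group-by-time design is ordinarily read through its interaction. The dilution would arise only if the main effect were used.

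**Scope.** The point covers the reaction-time and oculomotor measures, not every outcome. The available text of section (8) describes no reaction-time test, so its pre-season measurement is inferred from the time factor in the analysis paragraph.

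**Conclusion.** The point holds as one of efficiency and clarity. Under randomisation the planned interaction test is valid. It is less precise than adjustment for the pre-season value at every r below 1, by a factor of (1+r)/2 in variance. That costs about a third more athletes at r = 0.5 and about a twentieth more at r = 0.9. These figures rest on equal variances at the two visits, individual randomisation and an assumed r, and they ignore team clustering. They apply to device versus no device only, because the concussion group is formed after baseline and is not randomised. The documents do not support calling the planned test biased or wrong. The change is worth making because it needs no new data and also removes the inconsistency between the general Analysis of Covariance statement and the two ANOVA paragraphs.

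**What to change.** Reconcile the Statistical analyses, Simple Reaction Time and Oculomotor Measures paragraphs with wording such as:

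*For each reaction-time and oculomotor measure, the device versus no-device effect is the coefficient of allocated arm in a linear model of the post-season value on arm and the pre-season value of the same measure, reported with its 95% confidence interval. For pursuit measures the pre-season value is that of the same task condition. If teams are the unit of allocation, the model accounts for team.*

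Correct the Analysis of Covariance sentence so that it names the pre-season value as the covariate. Keep the mixed ANOVA, including the concussion group, as a supporting analysis, and state which of its terms is of interest.

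The cost is wording only. The small downsides are reliance on a roughly linear relation to the pre-season value, which the plan's existing linearity checks can cover, and possible divergence from the change-score result if the arms were not formed at random. Keeping the ANOVA would show any such divergence.
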